5.4 Duration of Therapy

In the absence of treatment delays due to adverse events, treatment may continue until one of the following criteria applies:

1. Clinically significant progressive disease, or
2. Intercurrent illness that prevents further administration of treatment, or
3. Patient request, or
4. General or specific changes in the patient's condition render the patient unacceptable for further treatment in the judgment of the investigator, or
5. Unacceptable toxicity that in the opinion of the investigator makes it unsafe to continue therapy.
 - 5.4.1 It is planned that up to a total of 24 cycles of therapy will be administered for patients deriving benefit from this regimen. Continuation of therapy for patients completing 24 cycles of therapy may be considered on a case-by-case basis after discussion with the principal investigator.
 - 5.4.2. A minimum of 1 full course (defined as the administration of 5-azacytidine for 7 days and one dose of lirilumab) will be required for a patient to be considered as having received an adequate trial to evaluate efficacy. All patients receiving at least one dose of any of the two drugs will be considered evaluable for toxicity.

5.5 Supportive Care:

Supportive care measures including blood products, infection prophylaxis and growth factors will be administered according to institutional and Leukemia Department guidelines.

Supportive care measures including blood products, infection prophylaxis and growth factors will be administered according to institutional and Leukemia Department guidelines.

Management Algorithms for Treatment of Lirilumab Related Adverse Events

Immuno-oncology (I-O) agents are associated with AEs that can differ in severity and duration than AEs caused by other therapeutic classes. Lirilumab is considered an immuno-oncology agent in this protocol. Early recognition and management of AEs associated with immuno-oncology agents such as lirilumab may mitigate severe toxicity. Lirilumab has a known safety profile however, a general principle is that differential diagnoses should be diligently evaluated according to standard medical practice. Non-inflammatory etiologies should be considered and appropriately treated. Corticosteroids are a primary therapy for immuno-oncology drug-related adverse events, and lirilumab is no exception. The oral equivalent of the recommended IV doses may be considered for

ambulatory patients with low-grade toxicities. The lower bioavailability of oral corticosteroids should be taken into account when switching to the equivalent dose of oral corticosteroids.

Management Algorithms have been developed to assist investigators in assessing and managing the following groups of adverse events: **Endocrinopathy, Gastrointestinal, Hepatic, Neurological Pulmonary, Renal and Skin**. These algorithms are found in the “Lirilumab Investigator Brochure” (Appendix E) and “Management algorithms for immuno-oncology drug-related adverse events” (Appendix G) of this protocol. The guidance provided in these algorithms should not replace the Investigator’s medical judgment but should complement it.

Finally, consultation with a medical or surgical specialist, especially prior to an invasive diagnostic or therapeutic procedure, is highly recommended.

5.6 Concomitant Medications:

Consistent with subject safety and comfort, administration of any prescription or over-the-counter drug products other than study medication should be minimized during the study period. Subjects should be discouraged from use of street drugs, herbal remedies, self-prescribed drugs, tobacco products, or excessive alcohol during the clinical study.

If considered necessary for the subject’s wellbeing, drugs for concomitant medical conditions or for symptom management may be given at the discretion of the investigator. The investigator’s decision to authorize the use of any drug other than study drug should take into account subject safety, the medical need, the potential for drug interactions, the possibility for masking symptoms of a more significant underlying event, and whether use of the drug will compromise the outcome or integrity of the study.

Subjects should be instructed about the importance of the need to inform the clinic staff of the use of any drugs or remedies (whether prescribed, over-the-counter, or illicit) before and during the course of the study.

Recommendations with regard to specific types of concomitant therapies, supportive care, diet and other interventions are as follows:

Concomitant medications are recommended as prophylaxis for nausea, vomiting, and infections, and are allowed for managing myelosuppression as shown in Table 3. Myelosuppression is expected in patients with AML due to underlying disease, as well as due to chemotherapy (such as 5-azacytidine), or both. Most patients have neutropenia, thrombocytopenia, or both at study entry. Significant or life-threatening myelosuppression may be managed with growth factor support including G-CSF, GM-CSF and platelet growth factors and erythropoietin/darbopoetin/blood transfusion according to institutional standard of

care, American Society of Clinical Oncology (ASCO) Practice Guidelines, and/or NCCN Practice Guidelines.

Infections secondary to myelosuppression are common in patients with AML, and may be related to underlying disease, chemotherapy, or both. Therefore, the use of prophylactic antibiotics, antifungal agents, and antiviral agents is recommended according to institutional standards.

Since the effect of both lirilumab and 5-azacytidine may be delayed for up to 4 weeks, patients with high WBC counts may receive hydroxyurea and up to 1 dose of cytarabine (up to 2 g/m²) prior to study entry. Hydroxyurea is allowed while the patient is on active study treatment, as needed, for clinical benefit and after discussion with the PI. Hydrea and cytarabine use would be recorded in the CRF. Concurrent therapy for CNS prophylaxis or continuation of therapy for controlled CNS disease is permitted. With the exception of these agents, concomitant systemic chemotherapy or radiation therapy is not permitted. Subjects are not allowed to participate concurrently in any other therapeutic clinical study.

Subjects may be receiving systemic corticosteroids (daily doses ≤10 mg of prednisone or equivalent if indicated for adrenal replacement or antiemetic therapy), topical, or inhaled corticosteroids at study enrollment. They may receive systemic, topical, inhaled, or enteric corticosteroids while on study without limitation if they develop conditions that require corticosteroid therapy; such subjects are not required to discontinue study participation.

All ongoing medications and therapies (including herbal products, nutritional supplements, and nontraditional medications) at screening will be considered prior medications. Concomitant medication data will not be collected or entered into the case report form other than hydrea and cytarabine as mentioned above; however, the subject's medication record will contain a list of concomitant medications. If a prohibited medication is inadvertently administered/ taken by the patient, the patient may remain on study as long as the prohibited medication is discontinued as soon as feasible. If a prohibited medication is considered essential for the patient well being, continuation on study with concomitant administration of such medication(s) will need to be discussed with and approved by principal investigator and medical monitor. Prohibited medications are shown in Table 3.

Table 3: Instructions for the use of concomitant medications and therapies

Category of Use	Medication	Comment on Use	Restriction on Use
Recommended	Prophylactic antibiotics, antifungal agents, and antiviral agents	Strongly encouraged	None
	Antiemetic agents	According to standard of care at MDACC	None
Allowed	Oral allopurinol or rasburicase	At investigators discretion	None
	Leukapheresis	According to standard of	Before induction 1 day 1

		care at MDACC	only
	Red blood cell transfusion	None	None
	Platelet transfusion	None	None
	White blood cell transfusion	At investigators discretion according to standard of care at MDACC	None
	Myeloid growth factors or platelet growth factor	At investigators discretion according to standard of care at MDACC	None
	Erythropoietin or darbepoetin	At investigators discretion	None
	Any other medication for supportive care	At investigators discretion according to standard of care at MDACC	None

MDACC = MD Anderson Cancer Center

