4.1 Inclusion Criteria

- 4.1.1 Patients with AML or biphenotypic or bilineage leukemia who have failed at least one prior therapy. Patients with AML should have failed prior therapy

or have relapsed after prior therapy.

- 4.1.2 Patients should not be eligible or able to receive approved therapy of confirmed clinical benefit in this patient population
- 4.1.3 Patients with MDS or CMML who received therapy for the MDS or CMML and progress to AML are eligible at the time of diagnosis of AML regardless any prior therapy for AML. The WHO classification will be used for AML.
- 4.1.4 Prior therapy with hydroxyurea, chemotherapy, biological or targeted therapy (e.g. FLT3 inhibitors, other kinase inhibitors), or hematopoietic growth factors is allowed.
- 4.1.5 Age ≥ 18 years.
- 4.1.6 Eastern Cooperative Oncology Group (ECOG) Performance Status ≤ 2 .
- 4.1.7 Adequate organ function: total bilirubin ≤ 2 times upper limit of normal (\times ULN) ($\leq 3 \times$ ULN if considered to be due to leukemic involvement or Gilbert's syndrome); aspartate aminotransferase or alanine aminotransferase $\leq 2.5 \times$ ULN ($\leq 5.0 \times$ ULN if considered to be due to leukemic involvement); serum creatinine $\leq 2 \times$ ULN or GFR ≥ 50
- 4.1.8 Patients must provide written informed consent
- 4.1.9 In the absence of rapidly progressing disease, the interval from prior treatment to time of initiation of 5-azacytidine and lirilumab will be at least 2 weeks OR at least 5 half-lives for cytotoxic/noncytotoxic agents. Use of one dose of cytarabine (up to 2 g/m²) is allowed prior to the start of study therapy or hydroxyurea for patients with rapidly proliferative disease is allowed before the start of study therapy and while the patient is on active study treatment, as needed, for clinical benefit and after discussion with the PI. Concurrent therapy for CNS prophylaxis or continuation of therapy for controlled CNS disease is permitted
- 4.1.10 Females must be surgically or biologically sterile or postmenopausal (amenorrheic for at least 12 months) or if of childbearing potential, must have a negative serum or urine pregnancy test within 72 hours before the start of the treatment

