7.1 Pre-Treatment Evaluation

All pretreatment studies should be obtained within 14 days of entry into the trial, unless otherwise stated.

7.1.1 A complete history and physical, documentation of all measurable disease, concomitant medications and performance status.

7.1.2 CBC, platelet count, differential (differential can be omitted if WBC is $\leq 0.5 \times 10^9/L$).

7.1.3 Creatinine, total bilirubin, ALT or AST.

- 7.1.4 Pregnancy test (urine or plasma) in females of childbearing potential should be performed within 72 hours before initiation of study.
- 7.1.5 Bone marrow aspirate during the last 28 days preceding study initiation. Cytogenetics will be obtained prior to therapy (results from prior analysis can be used for this purpose).
- 7.1.6 Pretreatment optional correlative studies (see below)

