Treatment may be discontinued for a variety of reasons, including patient withdrawal, investigator decision, and reasons specified by the protocol. Reasons for discontinuation of treatments are described below.

7 CRITERIA FOR RESPONSE:

Response Criteria for AML

Response criteria will be modified from the International Working Group for AML (JCO 2003; 21: 4642-9)[56]. Responders are patients who obtain a CR, CRi, or PR, with or without cytogenetic response, hematologic improvements, and morphologic leukemia-free state. Briefly, criteria are as follows:

8.1.1 Complete remission (CR):

- ◆ Peripheral blood counts:
No circulating blasts
Neutrophil count $\geq 1.0 \times 10^9/L$
Platelet count $\geq 100 \times 10^9/L$
- ◆ Bone marrow aspirate and biopsy:
 $\leq 5\%$ blasts
No Auer rods
No extramedullary leukemia

8.1.2 Complete Remission with Incomplete Platelet Recovery (CRp):

For patients to be classified as being in CRp, they must achieve CR except for incomplete platelet recovery ($< 100 \times 10^9/L$).

8.1.3 Complete remission with incomplete blood count recovery (CRi):

- ◆ **Peripheral blood counts:**
No circulating blasts
Neutrophil count $< 1.0 \times 10^9/L$, or
Platelet count $< 100 \times 10^9/L$
- ◆ **Bone marrow aspirate and biopsy:**
 $\leq 5\%$ blasts
No Auer rods
No extramedullary leukemia

8.1.4 Partial remission:

- ◆ All CR criteria if abnormal before treatment except:
- ◆ $\geq 50\%$ reduction in bone marrow blast but still $> 5\%$

8.1.5 Morphologic leukemia-free state:

- ◆ Bone marrow: $\leq 5\%$ myeloblasts

8.1.6 Hematologic Improvement (HI): Hematologic response must be described by the number of positively affected cell lines.

- ◆ **Erythroid response (E)** (pretreatment Hgb < 11 g/dL)
Hgb increase by ≥ 1.5 g/dL
- ◆ **Platelet response (P)** (pretreatment platelets $< 100 \times 10^9/L$)
Absolute increase of $\geq 30 \times 10^9/L$ for patients starting with $> 20 \times 10^9/L$ platelets
Increase from $< 20 \times 10^9/L$ to $> 20 \times 10^9/L$ and by at least 100%
- ◆ **Neutrophil response (N)** (pretreatment ANC $< 1.0 \times 10^9/L$)
At least 100% increase and an absolute increase $> 0.5 \times 10^9/L$
- ◆ **Blast response (B)**
 $\geq 50\%$ reduction in peripheral blood or bone marrow blasts but still $> 5\%$

9 DISCONTINUATION OF TREATMENT:

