11.1 Sample Size

Part a. Lead-in phase

The primary objective of the lead-in phase is to determine the safety of lirilumab in combination with 5-azacytidine in patients with refractory/ relapsed AML. Up to 24 patients will be accrued into lead-in part of the study.

Part b. Phase II

Up to 40 patients (including 6 patients treated at the MTD from the lead-in part) will be recruited for the Phase II part.

The primary objective of the phase II is to determine the efficacy of lirilumab in combination with 5-azacytidine in patients with refractory, relapsed or untreated AML. The efficacy of the combination will be measured by the overall response rate (ORR), defined as CR (complete remission) + CRp (complete remission with incomplete platelet recovery) + CRi (complete remission with incomplete count recovery) + PR (partial response) + marrow clearance of blasts + HI (Hematological improvement) within 3 months of treatment initiation among adult patients with refractory/ relapsed AML. ORR and toxicity will be monitored simultaneously using the Bayesian approach of Thall, Simon, Estey (1995, 1996) and the extension by Thall and Sung (1998).

Once safety of the MTD has been established, any patients still on study at a dose lower than MTD can be dose escalated up to MTD. Patients treated in the lead-in phase at MTD will be included in the phase II portion of the study.

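### A halving of blasts under permitted hydroxyurea or after pre-study cytarabine can be scored as a response in the primary ORR, and no baseline rule or sensitivity analysis separates it out

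*Combined protocol and SAP*

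**What the plan says.** **Endpoint.** Section 11.1 defines ORR as CR, CRp, CRi, PR and marrow clearance of blasts plus "HI (Hematological improvement) within 3 months of treatment initiation". Under hematologic improvement, 8.1.6 lists a blast response: an at least 50% "reduction in peripheral blood or bone marrow blasts but still" above 5%. It asks for no repeat assessment, minimum duration or attribution.

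**Permitted cytoreduction.** Section 4.1.9 says "Use of one dose of cytarabine (up to 2 g/m²) is allowed prior to the start of study therapy". Section 5.6 repeats this and adds "Hydroxyurea is allowed while the patient is on active study treatment, as needed, for clinical benefit and after discussion with the PI". It sets no limit on hydroxyurea dose, duration or cycle. It also says "Hydrea and cytarabine use would be recorded in the CRF". More generally, 5.6 tells the investigator, before authorizing any non-study drug, to consider "whether use of the drug will compromise the outcome or integrity of the study".

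**Baseline.** Section 7.1 says "All pretreatment studies should be obtained within 14 days of entry into the trial, unless otherwise stated"; this covers the blood count and differential. For the marrow, 7.1.5 says "Bone marrow aspirate during the last 28 days preceding study initiation". Neither has to follow cytoreduction.

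**Analysis.** Section 11.2 estimates ORR with a 95% confidence interval and also reports ORR over the whole study period. It scores patients who drop out before finishing all cycles as failures. It sets the result against a 10-15% history and a 30% target. No analysis uses the recorded hydroxyurea or cytarabine.

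**The concern.** Section 5.6 allows these drugs for patients with high white counts because the study drugs may take up to four weeks to work. Cytoreduction is thus expected to act early, inside the three-month response window. In cycles 1 to 3 a weekly differential (7.2.2) gives repeated chances to record one qualifying fall in blood blasts.

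If the fall came from hydroxyurea, or if the baseline was drawn before the cytarabine, 8.1.6 still scores a response and 11.1 still counts it. The trial has a single arm, so nothing in the comparison offsets it. Two results are at stake: the final ORR, and the Table 5 futility counts, where the bounds are only a few responses.

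**Working it through.** **1. Following the rule through.** Take a patient whose baseline sample is 10 days old, who receives cytarabine 5 days before day 1, and whose blood blasts have halved but stay above 5% at the first weekly count. Section 7.1 accepts the baseline, 4.1.9 accepts the cytarabine, 8.1.6 scores the fall and 11.1 counts it. No clause stops the sequence. The same holds for a fall first seen on hydroxyurea. The study-period ORR does not help: it changes the time window and keeps the blast response.

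**2. Reproducing the plan's stopping figures.** Exact binomial recursion over looks at 5, 10, ..., 35 patients, with toxicity and response independent:

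P(stop) = 1 - P(no toxicity stop) x P(no futility stop).

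Table 6 gives 0.3001 at toxicity 0.10 and ORR 0.15. Tables 4 and 5 as printed give 0.6227. Lowering each Table 5 bound by one response (0 at 10-15 patients, 1 at 20-25, 2 at 30-35) gives 0.3001, and the remaining toxicity-0.10 rows also match (0.1479, 0.0703, 0.0328, 0.0151, 0.0069). That mismatch is a separate matter. Here it means only that futility figures have to be shown under both sets of bounds.

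**3. Per patient, with no usage rate needed.** Suppose k of 40 are wrongly scored and the rest respond at 15%. The marker is 12/40, the smallest count whose exact 95% interval excludes 15% (12/40: 16.6-46.5%; 11/40: 14.6-43.9%).

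P = P(Bin(40 - k, 0.15) >= 12 - k)

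| k | P(at least 12/40) |
|---|---|
| 0 | 1.2% |
| 1 | 2.5% |
| 2 | 4.9% |
| 3 | 9.2% |

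**4. As a rate (assumed; the documents give none).** Let f be the share of all true non-responders wrongly scored. Observed ORR = p + (1 - p)f. For p = 0.15 and f = 0.05: 0.15 + 0.85 x 0.05 = 0.1925, or 40 x 0.85 x 0.05 = 1.7 patients. The futility columns use the response rule alone.

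| True ORR | f | Patients in 40 | Observed ORR | P(at least 12/40) | Futility stop, Table 5 as printed | Futility stop, bounds one lower |
|---|---|---|---|---|---|---|
| 15% | 0 | 0 | 15.0% | 1.2% | 62% | 30% |
| 15% | 2.5% | 0.85 | 17.1% | 3.2% | 53% | 22% |
| 15% | 5% | 1.7 | 19.3% | 6.9% | 45% | 16% |
| 15% | 10% | 3.4 | 23.5% | 21.3% | 30% | 9% |
| 10% | 0 | 0 | 10.0% | 0.04% | 84% | 56% |
| 10% | 2.5% | 0.9 | 12.3% | 0.2% | 74% | 43% |
| 10% | 5% | 1.8 | 14.5% | 0.9% | 64% | 32% |
| 10% | 10% | 3.6 | 19.0% | 6.4% | 46% | 17% |

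Only cytoreduced patients can be affected, so f = u x g, where u is the share of non-responders who are cytoreduced and g the share of those wrongly scored. If u were 25% (assumed), f of 2.5%, 5% and 10% would need g of 10%, 20% and 40%. The bottom row for each true ORR is therefore demanding.

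**5. The 10-patient look.** One added response moves 1/10 to 2/10 (stop to continue, as printed), or 0/10 to 1/10 (lower bounds). At a true ORR of 15% the chance of sitting exactly on the bound is 10 x 0.15 x 0.85^9 = 35% as printed, or 0.85^10 = 20% under the lower bounds.

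**The case against.** The strongest reply is that the effect is not demonstrated. The >5% floor suggests that blasts are read as a percentage. Hydroxyurea and cytarabine are allowed for high white counts or proliferative disease, and a lower total count need not halve the blast percentage. Nothing in the documents says how often it would. This stands: no size can be claimed.

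The dropout rule may also help. Up to 24 cycles are planned, and if leaving for progression counts as dropping out, a patient with a transient fall becomes a failure in the final ORR. The final-ORR figures above give no credit for that. But the term is undefined, and the rule is stated for the primary analysis, not for the interim counts.

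PI discussion and the study-integrity check govern whether a drug is given, not how a later blast fall is scored. Weekly differentials will often supply a repeat value, but the definition does not ask for one. The opening sentence of the response criteria could be read as making hematologic improvement only an accompaniment to CR, CRi or PR; 11.1 explicitly counts it.

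A reader might infer that the reported ORR will be inflated, or that the trial carries a false-positive rate of up to 21%. The documents support neither. They give no cytoreduction or effect rate. The plan is an estimate with an interval and states no success cut-off. The historical 10-15% may have been scored with the same blast rule and the same drugs, in which case part of the effect cancels; the documents do not say.

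**Conclusion.** The concern holds as a gap in the scoring rule, not as a demonstrated bias. The stated rules allow a blast fall due to permitted hydroxyurea or cytarabine to be counted as a response to the combination, and no planned analysis would show how often that happened. The size is unknown. The range shown runs from under one patient in 40 to about three and a half, and rests on assumed rates, on independent binomial responses and on no credit for the dropout rule. The interim effect needs no assumed rate: when the count sits on the bound at 10 patients, a single such response changes the decision. The change is worth making because it is cheap and would measure the effect.

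**What to change.** **(a) Section 8.1.6.** Measure a blood-blast response from the last differential taken before day 1 and after any pre-study cytarabine. No extra marrow is needed.

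**(b) Section 11.** Pre-specify a sensitivity ORR that treats two groups of blast-only hematologic improvements as non-responses: those first documented on hydroxyurea or shortly after it (interval set in advance by the sponsor), and those whose baseline sample predates cytarabine. Report it beside the primary ORR and, for information, at each Table 5 look.

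The primary ORR components and denominator do not change. Part (b) only informs the interim looks and does not alter a Table 5 decision; part (a) can change an interim count, but only for blood-blast responses.

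**Cost.** One sentence in 8.1.6 and one added analysis, with no change to treatment. Section 5.6 promises only that use of these drugs is recorded, and 10.3 keeps abnormal hematologic values off the case report form, so drug dates and differentials may have to be taken from the medical record. The sensitivity ORR may be lower than the primary and may miss a true early responder still on hydroxyurea.

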7.2 Evaluation During Treatment

- 7.2.1 Physical exam at the start of each cycle (\pm 4 days) and documentation of all concomitant medications.
- 7.2.2 CBC, platelet count, differential once weekly (\pm 4 days) for the first 3 cycles, then every 2-4 weeks (differential can be omitted if WBC is $\leq 0.5 \times 10^9/L$)
- 7.2.3 Creatinine, total bilirubin, ALT once weekly (\pm 4 days) for the first 3 cycles, then every 2-4 weeks.
- 7.2.4 Bone marrow aspiration on day 28 (\pm 7 days), then every 1-3 cycles. Bone marrow tests can be ordered more frequently if mandated by development of peripheral blood counts. No repeat bone marrow is necessary if nonresponse or progressive disease can be unequivocally diagnosed from peripheral blood tests or, in patients with a WBC < 0.3 if the bone marrow test is considered noncontributory by the investigator at any time point.
- 7.2.5 Concomitant medication data will not be collected or entered into the case report form except for concomitant hydroxyurea and cytarabine; however, the subject's medication record will contain a list of concomitant medications.
- 7.2.6 Correlative Studies relating to immunologic response: Tumor tissue, blood samples and bone marrow aspirate will be collected on a separate IRB approved laboratory protocol for immune monitoring as previously published[52-55], under the supervision of the Immunotherapy Platform (MDACC Protocol PA13-0291). Patients will be consented separately on the IRB approved consent for protocol PA 13-0291. Patients may participate in protocol 2014-0862 irrespective of whether they choose to participate on protocol PA 13-0291. In tumor tissues, immunohistochemical studies will be performed to evaluate tumor and immunological cell markers such as CD4 and CD8 T cells. In peripheral blood, we will also evaluate tumor and immune cell populations including but not limited to CD4 and CD8 T cells in pre and post therapy samples.
- 7.2.7

Peripheral blood up to 20 mL (within 24 hours) will be collected under an IRB-approved laboratory protocol for testing of biomarkers at the following time points

- Baseline (prior to 5-azacytidine dose), on day 8 (prior to lirilumab dose), and between days 21 to 28 on cycle 1 (done at MD Anderson).
- In each subsequent cycle blood samples will be obtained on day 1 (prior to 5-azacytidine dose) and day 8 (prior to lirilumab dose) when possible.
- Samples will be collected at progression whenever possible.

Bone Marrow:

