All patients who received any dose of the study agent will be included in the analysis for efficacy and safety. Demographic/clinical characteristics (including duration of response) and safety data of the patients will be summarized using descriptive statistics such as mean, standard deviation, median and range. For the primary efficacy analysis, we will estimate the ORR for the combination treatment, along with the 95% confidence interval. Patients who drop out of the study before completing all the cycles will be treated as “failures” for the primary analysis. ORR during the study period will also be presented with the 95% confidence interval. The association between ORR and patient’s clinical characteristics will be examined by Wilcoxon’s rank sum test or Fisher’s exact test, as appropriate. Toxicity type, severity and attribution will be summarized for each patient using frequency tables.

The distribution of time-to-event endpoints (DFS and OS) including overall survival and progression free survival will be estimated using the method of Kaplan and Meier. Comparisons of time-to-event endpoints by important subgroups will be made using the log-rank tests. Paired t-tests will be used to determine the immunological and molecular changes in the peripheral blood and bone marrow from baseline to the time of response, and to the time of disease progression. Correlation analysis (such as logistic regression analysis) will be conducted to determine the relationship between induction of hypomethylation / DNA damage and clinical response.

Statistical analysis of biomarker data: Descriptive statistics including plots, mean, median and standard deviations will be used to summarize data. For continuous outcomes, t-test and ANOVA will be used to compare outcome measures across patient characteristics. Dunnett’s and Tukey’s test that properly adjust for multiplicity in multiple tests will be implemented. Pair-wise comparisons will be performed using pre- and post-therapy samples from each patient . The chi-square test or Fisher’s exact test will be used to test the association between two categorical variables such as disease state and performance status. Both univariate and multivariate logistic regressions will be performed to model prognostic factors.

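### Steroid use on study is kept off the case report form and ignored in the paired immune-marker tests, so steroid and study-drug effects will be mixed unless exposure is abstracted and used

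*Combined protocol and SAP*

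**What the plan says.** At entry, systemic steroids are capped at 10 mg of prednisone or equivalent daily (exclusion 4.2.8 and section 5.6). On study the cap is lifted when there is a medical need: "They may receive systemic, topical, inhaled, or enteric corticosteroids while on study without limitation if they develop conditions that require corticosteroid therapy". Section 5.6 adds that such patients need not leave the study. Section 5.5 expects the need to arise: "Corticosteroids are a primary therapy for immuno-oncology drug-related adverse events, and lirilumab is no exception". Section 5.3.4 allows dosing to be interrupted for long steroid tapers and has leukemia assessments continue meanwhile.

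On recording, section 5.6 says "Concomitant medication data will not be collected or entered into the case report form other than hydrea and cytarabine as mentioned above", and the sentence goes on: "however, the subject's medication record will contain a list of concomitant medications". Section 7.2.5 repeats both halves. Section 7.2.1 asks for "documentation of all concomitant medications" with the physical examination at the start of each cycle.

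On analysis, exploratory objective 1.3.1 concerns immunological and molecular changes in response to the two study drugs. Section 7.2.6 names CD4 and CD8 T cells among the markers. Section 11.2 says: "Paired t-tests will be used to determine the immunological and molecular changes in the peripheral blood and bone marrow from baseline", with follow-up taken at response and at progression. Its biomarker paragraph adds: "Pair-wise comparisons will be performed using pre- and post-therapy samples from each patient". Neither passage mentions steroid exposure as a covariate, an exclusion or a sensitivity analysis.

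**The concern.** The baseline sample is drawn under a steroid cap and later samples are not. A patient treated with steroids for an immune-type event can stay on study and keep giving samples. If steroids move the markers, the within-patient change contains both a steroid part and a study-drug part. The study has a single arm, so no control group carries the steroid part. The plan already puts two concomitant drugs on the CRF, but not the one it names as primary treatment for lirilumab-related events. As planned, the analysis data set would not show which samples were affected.

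At stake is the reading of exploratory objective 1.3.1. A steroid-driven change could be reported as a pharmacodynamic effect of the combination, or could hide a real one.

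**Working it through.** The plan gives no sample size, SD, effect size, significance level or sidedness for the marker tests, so there is no stated figure to reproduce. The check has two parts.

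**1. The chain in the documents.**
- Steroid exposure at follow-up can exceed exposure at baseline (4.2.8 against 5.6).
- Steroid use is foreseen (5.5), and leukemia assessments continue during long tapers (5.3.4).
- Biomarker marrow samples are taken at day 28, then every 1 to 3 cycles and at progression (7.2.7), so sampling during steroid treatment is foreseeable.
- The CRF omits steroids (5.6, 7.2.5), and the tests have no term for them (11.2).
- The medication record lists concomitant drugs (5.6, 7.2.5) and they are documented each cycle (7.2.1), so exposure can be recovered from source. No abstraction step is planned, and the required detail (dose, dates) is not specified.

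**2. Illustrative size.** Assumptions: the study drugs have no effect; the SD of the paired change is 1; a fraction f of patients are on steroids at the follow-up sample; steroids shift the marker by d SD; the test is a two-sided 5% paired t-test. None of f, d, the test level or the 20-pair case comes from the documents. Forty pairs is the phase II maximum (11.1).

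The bias in the mean change is f × d. For f = 20% and d = 1 it is 0.20 × 1 = 0.20 SD, whatever the number of pairs.

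Simulated rejection rates (40,000 runs per cell, each patient exposed with probability f), shown for d = 0.5 and d = 1.0:

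| f | 40 pairs | 20 pairs |
|---|---|---|
| 0% | 4.9% / 4.9% | 5.0% / 4.9% |
| 10% | 6.1% / 8.9% | 5.4% / 6.9% |
| 20% | 9.3% / 20.4% | 6.9% / 11.9% |
| 30% | 14.6% / 38.7% | 9.3% / 21.1% |

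With a fixed number exposed and shifts of 1 and 2 SD, 40 pairs give 4.9% and 5.0% (1 exposed), 5.4% and 7.0% (2), about 8% and 15% (4), about 19% and 47% (8), and about 38% and 84% (12).

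The baseline-to-response test is smaller. At the 30% target response rate it has at most 0.30 × 40 = 12 pairs, and at 15% it has 0.15 × 40 = 6, before losses from optional samples. With 12 pairs the same shifts give about 5% (1 exposed), about 6% and 8% (2), and about 13% and 26% (4). The 40-pair rows are therefore a ceiling for the progression comparison and cannot describe the response comparison.

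**The case against.** A reader might infer that the steroid effect can never be separated and that the stored data rule out a correction. The documents do not support that. The sentence that excludes steroids from the CRF also says that the medication record lists concomitant drugs, section 7.2.1 has them documented each cycle, and section 12.0 keeps source data for at least 15 years. At a single centre with up to 40 phase II patients, abstraction is feasible. The immune-monitoring samples are also collected under a separate laboratory protocol (7.2.6), and whether that protocol records steroids cannot be seen from here.

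A reader might also take steroid use to be unrestricted. It is conditional on a medical need, and section 5.6 asks that concomitant drugs be kept to a minimum. Nor do the documents show that exposure falls mainly on patients with immune toxicity; that is an inference from section 5.5.

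Exposure may be rare. The nearest figure in the protocol is from the AML maintenance trial in section 2.4: 9 of 150 subjects (6%), on lirilumab or placebo, had related Grade 3 events, several of them cytopenias. This is only a rough guide, since steroids may be given for other reasons, but at such fractions the inflation is slight.

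Finally, an uncontrolled before-after test cannot assign a change to the study drugs even with steroids accounted for: hydroxyurea, growth factors, transfusions, infection and falling blast burden remain. Dropping on-steroid samples from the main analysis would also select on a possible consequence of treatment.

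All of this stands and sets the limits of the point. It does not remove the gap: no abstraction is planned and the analysis makes no use of exposure.

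**Conclusion.** The point holds in a limited form. The plan keeps a foreseen immunosuppressive co-treatment off the CRF and out of the marker analysis, so its effect will be mixed with that of the study drugs unless the medication record is abstracted and used.

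The size is unknown. Under the stated assumptions it is negligible if few patients are on steroids at sampling. It becomes material in the larger comparisons at about 20% or more, and is milder in the small response comparison. The documents give neither the fraction nor the shift, and that steroids move these markers at all is itself an assumption.

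Only an exploratory objective with optional samples is affected. The overall response rate, its monitoring, the dose-limiting toxicity assessment and the survival endpoints are untouched. Severity: minor.

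**What to change.** Add systemic corticosteroids (drug, daily dose, start and stop dates) to the hydroxyurea and cytarabine already entered on the CRF, taken from the existing medication record, and amend sections 5.6 and 7.2.5 to match. Nothing about when steroids may be given needs to change.

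In section 11.2:
- Keep the all-sample paired comparison as the main exploratory analysis.
- Flag samples drawn during systemic steroids above the protocol's own entry limit (10 mg prednisone-equivalent daily), and report how many there are.
- Pre-specify a sensitivity analysis that excludes or adjusts for flagged samples, noting that exclusion may favour patients without immune toxicity and that neither analysis makes a single-arm comparison causal.

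The cost is a few CRF fields, a little data entry and a short addition to section 11.2. Recording dose and dates as treatment proceeds should be more reliable than reconstructing them later from a list.
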